## **10.10 Procedures for Expedited Reporting**

### **Responsibility for Reporting SAEs to Health Canada**

Ozmosis, acting on behalf of Sponsor, will be responsible for notifying Health Canada in an expedited manner of adverse events which are considered *serious* and *unexpected* and *related* to the protocol treatment (or for which a causal relationship with the protocol treatment cannot be ruled out). Follow-up of SAEs as documented and submitted by the clinical site on the Ozmosis. SAE form will be forwarded to Health Canada by Ozmosis, where applicable.

### **Responsibility for Reporting SAEs (including Pregnancies as applicable) and AESIs to Sponsor**

Ozmosis Research Inc. will be responsible for submitting all SAEs and AESIs (initial and/or follow-up reports) to the Sponsor using the SAE Report Form and pregnancies using the Pregnancy Report Form. The form must be emailed to Sponsor at the latest within 24 hours after Ozmosis receives it from the site. The foregoing is applicable to all SAEs, irrespective of causality.

### **Reporting of SAEs to Local Ethics Boards**

SAEs occurring within a site should also be reported to local ethics boards according to their local policies.

Ozmosis will notify all PIs of all SAEs that are reportable to regulatory authorities in Canada from this trial or from other clinical trials as reported to the Sponsor. PIs (or their designee) must notify their ethics boards and file the report with their Investigator Site File.

Documentation that SAEs have been reported to REBs must be kept on file at the site and Ozmosis.

### **Reporting of SAEs to Pharmaceutical Company**

Ozmosis, acting on behalf of the Sponsor, will notify Sanofi of all reportable SAEs (i.e. SAEs requiring reporting to Health Canada), any misuse/abuse of ASC, or any ASC exposure during pregnancy within 15 days of receipt of reports from the sites.

## **10.11 Reporting of Pregnancy**

Pregnancies occurring in study patients/sexual partner(s) will be treated procedurally as SAEs. Pregnancies occurring in study patients or their sexual partner(s) after study treatment should be reported separately on Pregnancy Report Form and the patient has to discontinue the trial medications.

The outcome of all pregnancies (spontaneous miscarriage, elective termination, ectopic pregnancy, normal birth, or congenital abnormality) should be followed up and documented even if the patient was discontinued from the study.

Pregnancy in itself, occurring in female patients, and female partners of male patients is not regarded as an AE unless there is a suspicion that the IPs under study may have interfered with the effectiveness of a contraceptive medication.

The QIs are required to report to Ozmosis any pregnancy occurring in female patients, and female partners of male patients. Women of childbearing potential will be instructed to contact the investigator or study staff immediately if they suspect they might be pregnant (e.g. missed or late menstrual period) at any time during study participation.

The investigator must immediately notify Ozmosis if a study subject becomes pregnant and discontinue study. Any drug exposures during pregnancy must immediately be reported to Ozmosis, who will inform Sanofi Canada within 15 days.

## **11. STATISTICAL ANALYSIS**

The final analysis will be performed once all participants have either completed at least 52 weeks of treatment or discontinued study treatment prior to Week 52. Data from all participating centers will be pooled to ensure an adequate sample size for analysis. Demographic and baseline disease characteristics will be summarized descriptively. Categorical variables will be presented as frequencies and percentages, and continuous variables as mean, SD, median, minimum, and maximum; for selected parameters, the 25th and 75th percentiles will also be provided. Graphical summaries of the data may also be presented.

The number of participants with dose modifications (reductions, interruptions, or permanent discontinuations) and the corresponding reasons will be summarized. All dosing data will be listed. Categorical variables will be summarized as frequencies and percentages, while continuous variables will be summarized using mean, SD, median, 25th and 75th percentiles, minimum, and maximum.

All tests of treatment effects will be conducted at a 2-sided alpha level of 0.05, unless otherwise stated. Additional exploratory analyses of the data will be conducted as deemed appropriate.

There are no planned interim analyses for this study.

### **11.1 Study Design and Justification for Sample Size**

Based on the REACH3 study, the overall response rate with Ruxolitinib monotherapy was 49% at 6 months. Our null and alternative hypothesis was 49.7% and 66% of ORR at 6

months, respectively. For a sample size of 57 observations, a 2-sided exact test as the power calculation method will have 90% power to reject the null hypothesis assuming that the null proportion is 0.497, the alternative proportion is 0.66, and that the test is conducted at the alpha 10% significance level. Considering a 10% drop outs the study will enrol 63 pts.

If the number of patients achieving CR or PR at 6 months is 37 or more, the hypothesis that  $P \leq 0.497$  is rejected. Thus, success of the trial will be defined as 37 or more patients achieving CR or PR at 6 months out of 63 patients, which can be translated into a clinically meaningful improvement over standard care and within the expected safety profile. If the number of patients achieving CR/PR at 6 months is 36 or less, the hypothesis that  $P \geq 0.66$  is rejected, thus determined to be failure.

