	
End of Treatment Visit
 
 
• Physical Examination & ECOG
 
• Vital Signs
 
• Hematology
 
• Serum Chemistry
 
• AE Assessment
 
• Concomitant Medications
 
• NIH consensus based GvHD organ specific score and global severity score (i.e. mild vs moderate vs severe grade)
 
• Modified Lee Symptom Scale
 
• P-ROM (Photographic Range-Of-Motion) assessment
 
• Pulmonary Function Test
 
• IP return and accountability
 
• Correlative Samples
 
 
Follow-up Visit
 
 
• Survival status
 
• Concomitant Medications (new cGvHD therapies only)
 

Response:	
- Overall response rate (ORR) will be evaluated at 24 and 48 weeks after initiation of combination therapy
 
- Failure-free survival (FFS) will be evaluated using Kaplan-Meier method. The FFS rate will be evaluated at 24 and 48 weeks after initiation of combination therapy
 
- Durable response after response achievement will be evaluated only in the patients who achieved CR or PR during the treatment period (any response)

Safety Variables & Analysis:	
The safety and tolerability of study treatment will be evaluated by means of AE reports, physical examinations, and laboratory safety evaluations. Terminology Criteria for Adverse Events (CTCAE) V5.0 will be used for grading of AEs.
 
Interim safety data will be examined on an ongoing basis to ensure patient safety.

Statistical Analysis:	
Statistical Analysis: This is a single-arm phase II study with a sample size of 63 patients (accounting for 10% dropout) to provide 90% power to detect an improvement in ORR from 49.7% (null) to 66% (alternative) at 6 months using a two-sided exact test at <math>\alpha=0.10</math>
 
Populations:
 
 
- Intent-to-Treat (ITT): All enrolled patients.
 
- Safety: All patients receiving <math>\geq 1</math> dose of belumosudil.
 
- Efficacy: All patients completing <math>\geq 1</math> cycle of belumosudil with baseline assessment.
 

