## 11.3 Evaluation of Study Endpoints

### 11.3.1 Evaluation of the Primary and Secondary Endpoints

Overall response rate (ORR) will be evaluated at 24 and 48 weeks after combination therapy (i.e. 28 and 52 weeks after enrollment), respectively. The proportion of responders and its 95% confidence interval (using exact binomial methods) will be calculated.

Failure-free survival (FFS) will be evaluated using Kaplan-Meier method. The FFS rate will be evaluated at 24 and 48 weeks after combination therapy (i.e. 28 and 52 weeks after enrollment), The composite endpoint of failure is defined as 1) GvHD progression or loss of response requiring switch of systemic GvHD treatment, 2) relapse of primary hematologic disease and 3) non-relapse mortality.

Durable response after response achievement will be evaluated only in the patients achieved CR or PR (any response). The Kaplan-Meier estimate will be calculated from the date of CR/PR achievement to the date of losing response/progression or death from any cause.

GvHD symptom burden improvement, measured serially by the modified Lee Symptom Scale, will be evaluated using repeated measure based on the general linear model. If p-value is less than 0.05, it demonstrates statistically significant change over time within subject.

The Modified Lee symptom score (mLSS) will be used to reflect a symptom burden in cGvHD study patients. The symptoms will be assessed serially and will be evaluated using repeated measure based on the general linear model. If p-value is less than 0.05, it demonstrates statistically significant change over time within subject. The score assesses 7 different organs/areas including skin, eye/mouth, breathing, eating/digestion, muscle/joints, energy, and mental/emotional health. The sum of these domains will be calculated to derive the total mLSS. Clinically meaningful improvement in mLSS is defined as a reduction of  $\geq 7$  points in overall mLSS. Longitudinal change in mLSS is analyzed by repeated measures using generalized linear model over time, evaluating within-subject and between-subject effects. In addition, the proportion of the patients showing clinically meaningful improvement in mLSS is analyzed longitudinally at 12, 24, and 48 weeks. In addition, the best improvement in mLSS is also calculated in each subject and plotted.

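### The stated two-sided exact test at alpha 0.10 has 73–81% power at n=57, not 90%, and the 37-of-63 success rule is a one-sided 10% test that the stated test would not call significant

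*Protocol*

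**What the plan says.** Protocol Section 11.1 sets the design of the primary efficacy analysis, the overall response rate (ORR) at 24 weeks of combination therapy. The power statement begins "For a sample size of 57 observations" and claims that "a 2-sided exact test as the power calculation method will have 90% power to reject the null hypothesis". The rates compared are 0.497 under the null and 0.66 under the alternative, and the section specifies that "the test is conducted at the alpha 10% significance level". Enrolment is then raised to 63 to allow for 10% drop-out. The synopsis repeats the design for 63 patients, "to provide 90% power to detect an improvement in ORR from 49.7% (null) to 66% (alternative) at 6 months using a two-sided exact test", with the same alpha of 0.10.

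Section 11.1 also fixes the decision rule: "success of the trial will be defined as 37 or more patients achieving CR or PR at 6 months out of 63 patients". At 37 or more, a directional null (response rate no higher than 0.497) is said to be rejected. At 36 or fewer, a rate of 0.66 or higher is said to be rejected and the trial is a failure.

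For reporting, Section 11.3.1 says: "The proportion of responders and its 95% confidence interval (using exact binomial methods) will be calculated". No part of the protocol calls the primary test one-sided.

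**The concern.** Three statements about one analysis need to agree: the named test, the power claimed for it, and the responder count that triggers success. A two-sided test at alpha 0.10 leaves about 5% for the upper tail. A difference of 16.3 percentage points (66% − 49.7%) with 57 patients looks too small for 90% power at that level, and 37 of 63 (58.7%) looks too low a threshold.

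If so, a reader of the protocol would be misled twice. The chance of detecting the target effect with the named test would be well below 90%, and the chance of a false success would be nearly double the 5% that a two-sided 10% test implies. This is the only go/no-go rule for efficacy, so for some counts the trial could be called positive or negative depending on which sentence of Section 11.1 is followed.

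**Working it through.** **Inputs (Section 11.1 and synopsis).** p0 = 0.497; p1 = 0.66; alpha = 0.10, two-sided, exact; n = 57 for the power statement; 63 enrolled; success at 37 or more of 63; stated power 90%.

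**Formulas.** With X ~ Binomial(n, p) and rejection at X ≥ r:
- upper-tail type I error = P(X ≥ r | p0)
- power = P(X ≥ r | p1); under p1 the lower rejection region adds practically nothing.

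A two-sided exact test is usually built in one of two ways: equal tails (at most 0.05 in each), or a minimum-likelihood p-value (sum of the probabilities of all outcomes no more likely than the one observed). Both were tried.

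**Step 1: the stated 90% at n = 57**

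| Test at n = 57 | Reject at | Upper-tail error | Power |
|---|---|---|---|
| Two-sided 0.10, equal tails | ≥36 | 0.0283 | 72.6% |
| Two-sided 0.10, minimum likelihood (p = 0.085 at 35) | ≥35 | 0.0507 | 80.9% |
| One-sided 0.10, exact | ≥34 | 0.0851 | 87.5% |

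The stated 90% is not reproduced. The shortfall for the named test is 90 − 80.9 = 9.1 to 90 − 72.6 = 17.4 points. Two-sided normal approximations give 76% to 83%. Only one-sided 0.10 approximations come close at n = 57: 89.3% (null and alternative variances), 90.6% (alternative variance only) and 88.9% (arcsine). The 90% was therefore probably obtained from a one-sided 10% approximation.

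**Step 2: the same tests and the success rule at n = 63**

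| Responders of 63 | P(X ≥ r given 0.497) | Two-sided p (min. likelihood / doubled tail) | Power if this is the cut-off | Exact 95% CI |
|---|---|---|---|---|
| 36 | 0.1456 | 0.258 / 0.291 | 94.5% | 44.0–69.5% |
| 37 | 0.0953 | 0.167 / 0.191 | 91.0% | 45.6–71.0% |
| 38 | 0.0591 | 0.102 / 0.118 | 86.1% | 47.2–72.4% |
| 39 | 0.0347 | 0.059 / 0.069 | 79.5% | 48.8–73.9% |
| 40 | 0.0191 | 0.032 / 0.038 | 71.3% | 50.4–75.3% |

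- 37 is the smallest count with an upper tail of 0.10 or less, so the rule is the one-sided exact 10% test.
- The stated two-sided 0.10 test first rejects at 39, under either construction.
- The 95% interval first excludes 49.7% at 40.
- The interval that matches a one-sided 10% test is the two-sided 80% interval: 49.9% to 67.2% at 37 of 63, which just excludes 49.7%.

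**Step 3: what the stated test would need.** Two-sided exact power at alpha 0.10 first reaches 90% at 79 evaluable patients (minimum likelihood) or 82 (equal tails, 49 or more responders). Exact power is not monotone in n, so these are orders of magnitude and not firm requirements.

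**Step 4: sensitivity of the 91.0%.** It requires all 63 patients in the denominator. If only 57 are evaluable and the cut-off stays at 37, power is P(X ≥ 37 | 57, 0.66) = 62.8%, with type I error 1.5%.

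**The case against.** The best defence is that the decision rule is clear and works. Section 11.1 states a directional null, one cut-off, and a mirror rule for failure. At 63 the two errors are P(X ≥ 37 | 0.497) = 0.0953 and P(X ≤ 36 | 0.66) = 0.0899, about 10% each, as in a conventional single-stage phase II design. No lower-tail rejection is defined. On this reading the two-sided label is a slip, the 73–81% is the power of a test the rule never uses, and the conflict affects only the counts 37 and 38, the latter a near miss at p = 0.102.

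That reading of the rule stands, and it is why the repair is cheap. It does not remove the error. The synopsis and Section 11.1 both name a two-sided test, neither mentions a one-sided one, and Section 11.1 says the null is rejected at 37 when the test it names does not reject there. Because sidedness, alpha, power and threshold are all stated in the protocol and conflict with each other, this is not detail left to a later analysis plan.

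A second objection is that the 95% interval is for estimation only, and that pairing it with a 10% decision level is common. That is fair: the protocol does not make the interval a criterion. The point is limited to saying so, because at 37 to 39 responders the published interval will contain the ruxolitinib benchmark beside a declared success.

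A third is that writing 91.0% into the protocol without conditions would be optimistic. This stands too. Assuming, for illustration, that 10% drop out and count as non-responders, the effective rate is 0.66 × 0.9 = 0.594, and power at 37 of 63 is 59.6%.

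**Conclusion.** The concern holds. The stated test, the stated power and the stated threshold cannot all be true. The two-sided exact test at alpha 0.10 has 72.6% or 80.9% power at 57 patients, depending on its construction, and 79.5% at 63, against the 90% claimed. The 37-of-63 rule is a one-sided 10% test with type I error 9.5% and power 91.0%. At 37 or 38 responders the protocol declares success where its named test is not significant.

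These figures use only the protocol's own inputs and exact binomial probabilities. The figures at 63 assume that every enrolled patient is in the denominator. The operative design is coherent if described as one-sided. What is wrong is the description, but the description decides the conclusion at two possible counts of the primary endpoint, so it must be corrected before those counts are known.

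**What to change.** Choose one of these and write it identically in Section 11.1 and the synopsis:

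1. **Keep the rule and correct the test.** State a one-sided exact binomial test at alpha 0.10, n = 63, success at 37 or more, actual type I error 9.5%, and power 91.0% on the condition that all 63 are analysed. In Section 11.3.1, report the matching two-sided 80% exact interval beside the 95% interval, and say that the 95% interval is not the decision criterion.
2. **Keep the test and correct the rule.** If two-sided alpha 0.10 is meant, set success at 39 or more of 63 and state 79.5% power.

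Under either option, drop or recompute the 90% attached to 57 observations, and say how patients who drop out enter the count of 63.

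The cost is wording only, with no added patients. Under option 1 the stated error standard looks less strict; under option 2 the stated power falls by about 10 points. Choosing between them after the responder count is known would be post hoc.

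### The 90% power statement contradicts the success rule: the named two-sided 10% exact test gives 73–81% power, while 37 of 63 is a one-sided 10% rule with 91% power

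*Protocol*

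**What the plan says.** Section 11.1 of the protocol gives every input. The hypotheses are a null response rate of 0.497 and an alternative of 0.66 at 6 months ("assuming that the null proportion is 0.497, the alternative proportion is 0.66"). The size is introduced with "For a sample size of 57 observations", the level with "the test is conducted at the alpha 10% significance level", and the claim is that "a 2-sided exact test as the power calculation method will have 90% power to reject the null hypothesis". A 10% dropout allowance then takes enrolment to 63.

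The next paragraph of 11.1 fixes the decision rule on the enrolled number: "success of the trial will be defined as 37 or more patients achieving CR or PR at 6 months out of 63 patients". At 37 or more the hypothesis P ≤ 0.497 is rejected. At 36 or fewer P ≥ 0.66 is rejected and the trial has failed.

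The synopsis describes a single-arm study of 63 patients, dropout included, sized "to provide 90% power to detect an improvement in ORR from 49.7% (null) to 66% (alternative) at 6 months using a two-sided exact test" at alpha 0.10. So 11.1 puts the 90% on 57 patients, the synopsis puts it on 63, and both call the test two-sided.

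**The concern.** Test, level, sample size, cut-off and power are five linked quantities: once the first three are set with the two response rates, the other two follow. Here the stated power does not follow from the stated test at either sample size, and the stated cut-off does not follow from it either.

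What is at stake is the error rate of the primary efficacy decision. A reader told that the test is two-sided at 10% takes the chance of declaring success for a regimen no better than 49.7% to be at most 5%. The counting rule allows nearly double that. For two possible results, 37 and 38 responders, the rule and the named test disagree.

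**Working it through.** **Inputs** (all from 11.1): p0 = 0.497, p1 = 0.66, n = 57 evaluable, 63 enrolled, alpha = 0.10, success at 37 or more of 63. With X the number of responders, the upper-tail size of a cut-off c is P(X ≥ c | n, p0), and its power is P(X ≥ c | n, p1).

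**1. Where the 90% comes from.** At n = 57 the nearest match is a one-sided 10% normal approximation:

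Φ[(0.66 − 0.497 − 1.2816·√(0.497·0.503/57)) / √(0.66·0.34/57)] = Φ[(0.163 − 0.0849)/0.0627] = Φ(1.245) = 89.3%.

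With 5% in the upper tail the same formula gives 80.6%. The stated figure is therefore approached at 57 only by a test that is neither exact nor two-sided.

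**2. Exact tails**

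| n | cut-off | upper tail at 0.497 | power at 0.66 |
|---|---|---|---|
| 57 | 34 | 8.51% | 87.5% |
| 57 | 35 | 5.07% | 80.9% |
| 57 | 36 | 2.83% | 72.6% |
| 57 | 37 | 1.48% | 62.8% |
| 63 | 37 | 9.53% | 91.0% |
| 63 | 38 | 5.91% | 86.1% |
| 63 | 39 | 3.47% | 79.5% |

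**3. The test as named (two-sided exact, 10%)**
- n = 57, equal tails: the upper tail may not exceed 5%. A cut-off of 35 just misses (5.07%), so it is 36 and power is **72.6%**.
- n = 57, minimum-likelihood p-value: 35 of 57 gives p = 0.085 and rejects; 34 does not. Power is **80.9%**.
- n = 63: both versions need 39. Power is **79.5%**.

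**4. The rule as stated (at least 37 of 63).** Its upper tail is 9.53%, its power is 91.0%, and P(X ≤ 36 | 63, 0.66) = 9.0%. These are the properties of a one-sided 10% exact test on 63 patients. By the same calculation 63 is the smallest n at which that test reaches 90% power.

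**5. Where the rule and the named test disagree.** Two-sided minimum-likelihood p-values at n = 63 are 0.167 for 37, 0.102 for 38 and 0.059 for 39. Doubling the upper tail gives 0.191, 0.118 and 0.069. On either version 37 and 38 do not reject at 10%, yet the rule calls both a success.

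**6. Dropout.** The 91.0% and 79.5% need a 66% response rate over all 63 enrolled, but 63 already includes the 10% allowance (57 × 1.1 = 62.7). Suppose instead that 66% applies to those who remain and dropouts count as non-responders:
- exactly 57 able to respond, cut-off 37: power 62.8%;
- each of 63 with a 10% chance of dropping out, effective rate 0.9 × 0.66 = 0.594, cut-off 37: P(X ≥ 37 | 63, 0.594) = 59.6%.

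For a cut-off of 39 the same two assumptions give 40.8% and 39.4%.

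**The case against.** The strongest reply is that the operative text is the count, not the label. Section 11.1 states a one-sided null, a denominator of 63 and a cut-off of 37. That rule has 91.0% power and a 9.0% chance of a failure verdict at 66%. The synopsis also attaches the 90% to 63. On this view the design is a coherent one-sided 10% plan, and only the words two-sided and the figure 57 are out of place.

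Most of this stands. A reader might infer from the 73–81% that the trial is planned on a power it does not have, or that it carries a 19–27% chance of missing the target effect. The protocol does not support that: those figures belong to cut-offs of 35 or 36 of 57, which it never uses to judge the trial.

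The reply does not rescue the text. Both sections name a two-sided test, and 11.1 assigns the power to 57 observations. Even a one-sided 10% exact test at 57 reaches only 87.5%. Reading the 90% into the rule changes both the sidedness and the sample size that 11.1 states, and it spends the dropout allowance. This is also not detail left to a statistical analysis plan: every conflicting figure is printed in the protocol.

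**Conclusion.** The power statement in 11.1 and the synopsis is wrong as written and contradicts the decision rule in 11.1. Under the named test power is 72.6% or 80.9% at 57, depending on how two-sided is defined, and 79.5% at 63. The shortfall against 90% is about 9 to 17 points, too large for rounding.

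The main consequence is on type I error. The rule carries 9.5% in the upper tail, about twice the 5% implied by the label, and it declares success at 37 and 38 of 63 where the named test does not reject. The 90% itself is recoverable as a one-sided 10% exact test on 63, provided that the 66% rate holds across all 63 enrolled. If it holds only among those who stay and dropouts count as failures, power at the cut-off of 37 is about 60–63%. The arithmetic is exact and uses only the protocol's own inputs; the dropout range rests on the two assumptions shown.

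**What to change.** Amend the sample-size text in 11.1 and the synopsis, before any response data are seen, to one of these:

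- **(a)** One-sided exact test, alpha 0.10 (actual 9.5%), n = 63, success at 37 or more, power 91.0%. Delete the 57-observation claim.
- **(b)** Two-sided exact test, alpha 0.10, n = 63, success at 39 or more, power 79.5%. Change the failure limit to 38 or fewer.

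In either case state that the power assumes a 66% response rate over all 63 enrolled, with dropouts kept in the denominator, and give the lower power if dropouts are non-responders (about 60–63% for the cut-off of 37 with 10% dropout). If the primary analysis is to be on evaluable patients instead, give the cut-off for the actual denominator; for example, one-sided 10% at n = 57 needs 34 or more and has 87.5% power.

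The cost is a few sentences and no extra patients. The price is in the claim: it becomes openly one-sided under (a), or less favourable under (b). Keeping both the two-sided 10% test and 90% power would need more patients: 90% is first reached at 79 evaluable (minimum likelihood) or 82 (equal tails), and holds for every n from 86.

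### Section 11.1 says 36 or fewer responders rejects an ORR of 66%; on 63 patients that holds only at one-sided 10%, not at the labelled two-sided 10% level or against the planned 95% CI

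*Protocol*

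**What the plan says.** Protocol section 11.1 sets the hypotheses: "Our null and alternative hypothesis was 49.7% and 66% of ORR at 6" months. It describes the power calculation as follows: "For a sample size of 57 observations, a 2-sided exact test as the power calculation method will have 90% power", with the level given as "the test is conducted at the alpha 10% significance level". The Synopsis repeats the two-sided 10% label. Enrolment is then inflated: "Considering a 10% drop outs the study will enrol 63 pts".

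The decision rule has one cut-off and no middle zone. Success is 37 or more responders out of 63, which rejects P ≤ 0.497, where P is the true ORR. For the other side the section reads "If the number of patients achieving CR/PR at 6 months is 36 or less, the hypothesis that" P ≥ 0.66 is rejected, and the trial is classed as a failure. Only the success sentence names the denominator of 63.

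Section 11.3.1 fixes how the ORR is reported: "The proportion of responders and its 95% confidence interval (using exact binomial methods) will be calculated".

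**The concern.** The failure sentence does more than say the criterion was missed. It says the target ORR of 66% has been rejected. Section 11.1 gives no level for that second rejection, so a reader will apply the level it does state, two-sided 10%, or the interval printed with the estimate, 95%. If the claim fails at those levels, a report could say that the combination was shown not to reach 66% beside an interval that still includes 66%. The pass or fail decision is not at stake, because 36 or fewer is a failure either way. What is at stake is what the trial may conclude about the target effect after a near miss.

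**Working it through.** **Inputs.** Null ORR 0.497, target ORR 0.66, cut-off 37, denominator 63, and 57 observations for power (all section 11.1); exact two-sided 95% CI (section 11.3.1). X is the number of responders, binomial(n, P). Intervals are Clopper-Pearson.

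**Step 1: reproduce the plan's rule on 63.**
- P(X ≥ 37 | 0.497) = 0.0953. For 36 it would be P(X ≥ 36 | 0.497) = 0.1456, so 37 is the smallest cut-off with one-sided error at or below 10%.
- P(X ≤ 36 | 0.66) = 0.0899, so power is 1 − 0.0899 = 0.910.

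The cut-off therefore reproduces as a one-sided 10% rule on 63. As a two-sided 10% test with 5% per tail it would need 39: P(X ≥ 38 | 0.497) = 0.059 and P(X ≥ 39 | 0.497) = 0.035. The stated 90% power for 57 observations with a two-sided exact 10% test does not reproduce (72.6% with equal tails, 80.9% with the minimum-likelihood region). That is a separate matter and is not needed here.

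**Step 2: test 66% at the failure counts, n = 63.**

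| Responders | ORR | P(X ≤ x given 0.66) | 90% CI upper limit | 95% CI |
|---|---|---|---|---|
| 36 | 57.1% | 0.090 | 67.8% | 44.0% to 69.5% |
| 35 | 55.6% | 0.055 | 66.3% | 42.5% to 68.1% |
| 34 | 54.0% | 0.032 | 64.8% | 40.9% to 66.6% |
| 33 | 52.4% | 0.017 | 63.3% | 39.4% to 65.1% |

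- At one-sided 10%, all of these reject 66%.
- At 5% per tail, 35 and 36 do not.
- The 95% CI contains 66%, and also 49.7%, at 34, 35 and 36. At 33 or fewer it excludes 66%.

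One qualification: a two-sided p-value built by the minimum-likelihood method is 0.145 at 36 and 0.085 at 35. So 36 fails to reject under either construction, while 35 fails only with equal tails.

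**Step 3: the success side, n = 63.** The 95% CI lower limits are 45.6% at 37, 47.2% at 38 and 48.8% at 39, all below 49.7%. At 40 the limit is 50.4%. So three successful counts also disagree with the planned interval.

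**Step 4: an interval that matches the rule.** The two-sided 80% exact CI is 48.3% to 65.6% at 36/63, which excludes 66%. At 37/63 it is 49.9% to 67.2%, which excludes 49.7%. It agrees with both decisions.

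**Step 5: how likely the disputed failure counts are.** P(34 ≤ X ≤ 36) with n = 63 is 7.2% if the true ORR is 66%, 23.2% if it is 60% and 19.5% if it is 49.7%.

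**Step 6: sensitivity to the denominator.** This assumes that the cut-off stays at 36 while fewer patients are counted, each responding with probability 0.66. P(X ≤ 36 | 0.66) is 9.0% at n = 63, 19.8% at n = 60 and 37.2% at n = 57.

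**The case against.** The strongest reply is that this is an ordinary single-stage design with two hypotheses. One cut-off on 63 patients carries an error of 9.5% at the null and 9.0% at the target. Rejecting 66% at 36 or fewer is then a decision with a controlled error, slightly stricter than the one made at 37. The exact 95% CI is reported in any case, so a reader would see that 66% is not excluded at 34 to 36. All of this stands. It limits the point to mismatched levels: a one-sided 10% rule, a two-sided 10% label and a 95% interval.

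Three stronger readings are tempting, and the protocol does not support them.

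- *That section 11.1 takes a non-significant result as proof.* It states a test decision, and on 63 patients that decision has a 9.0% error.
- *That a result of 36 of 57 shows the sentence to be plainly false.* The figure of 57 belongs to the power sentence. The success rule is defined on 63, and section 11.2 defines the ITT population as all enrolled patients. Carrying the cut-off to 57 tests a rule the protocol does not state.
- *That 37.2% is also the false-rejection rate when six dropouts count as non-responders.* If the other 57 respond at 66%, the ORR over all 63 is 0.66 × 57/63 = 59.7%. P ≥ 0.66 is then false, and rejecting it is no error.

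**Conclusion.** The concern holds in a limited form. The claim that 36 or fewer responders rejects 66% is correct only at one-sided 10% with all 63 in the denominator, and section 11.1 does not state that level. At the labelled level, read as 5% per tail, it is not supported at 35 and 36 of 63. Against the planned 95% CI it is not supported at 34, 35 and 36. The success side is off in the same way at 37 to 39, so this is not a fault of the failure sentence alone.

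The denominator figures (19.8% at 60, 37.2% at 57) are conditional. They show that the rejection of 66% would no longer hold even at one-sided 10% if patients were dropped from the count with the cut-off unchanged. They do not describe the rule as written for 63. The pass or fail decision is unaffected; only the stated inference changes.

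**What to change.** Either of two edits to section 11.1 resolves it.

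1. Replace the failure sentence with: *If 36 or fewer of the 63 enrolled patients respond, P ≤ 0.497 is not rejected and the efficacy criterion is not met.* Drop the statement that P ≥ 0.66 is rejected.
2. Keep both rejections. State that each is a one-sided 10% test on all 63 enrolled patients, with actual errors of 9.5% and 9.0%. Correct the two-sided label here and in the Synopsis, and report the two-sided 80% exact CI beside the 95% CI.

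Requiring the 95% bound before 66% is called excluded, while leaving success at one-sided 9.5%, would be lopsided and is not advised.

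Neither edit needs more patients or data, and neither moves the cut-off. With the first, some negative results are described as missing the criterion rather than as excluding 66%. With the second, the stated error level looks less strict.
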